## 12.1. **$^{68}\text{Ga}$ -PSMA-HBED-CC PET Results Definition**

Imaging interpretation  $^{68}\text{Ga}$ -PSMA-HBED-CC PET:

**Local Interpretations:** PET images will initially be interpreted by a board certified nuclear medicine physician or a board-certified radiologist experienced in reading PET at the time of the imaging study at the institution that the study is being performed. These interpretations will not be used for evaluation of the primary endpoint.

**Blinded Read Logistics:** Imaging data will be de-identified. PET data will be interpreted by two different readers in a random order at separate reading sessions. Cross sectional imaging (CT or MRI) from the  $^{68}\text{Ga}$ -PSMA-HBED-CC PET will be available for anatomic correlate. The blinded readers will be blinded to all other imaging results and all other clinical data.

**Reader Positivity and Negativity Definition:** Sub-regions defined in Table 12.2 will be graded for the presence of suspected disease on a two-point scale by each reader (0=Negative or 1=Positive). A region will be judged as positive if at least one lesion in this region is visually positive..

### 12.1.1. Criteria for visual interpretation:

Sub-regions of suspected disease will be graded on a two-point scale by each blinded reader (0=Negative or 1= Positive). A region will be judged as positive if at least one lesion in this region is visually positive.

12.1.1.1. Lymph nodes will be considered positive if the  $^{68}\text{Ga}$ -PSMA-HBED-CC uptake is focal and greater than blood pool (adjacent or mediastinal blood pool).

- Lymph nodes will be classified further by region: pelvic, retroperitoneal, thoracic and other. Additionally, pelvic lymph nodes will be sub-classified according to their localization as follows: R/L obturator, R/L external iliac, R/L internal iliac and other (total of 7 subgroups). These pelvic sub-regions will be correlated with reference standard results in these sub-regions, however this sub-region data will not be directly used for evaluation of the primary or secondary endpoints, but for exploratory analysis.

12.1.1.2. Visceral lesions will be considered positive if the  $^{68}\text{Ga}$ -PSMA-HBED-CC uptake is focal and greater than physiologic background activity of the involvement organ or anatomic site.

- Visceral lesions will be classified further by major organ: lung, liver, pancreas... as defined in Table 2. These sub-regions will be correlated with reference standard results in these sub-regions, however this sub-region data will not be directly used for evaluation of the primary or secondary endpoints, but for exploratory analysis.

12.1.1.3. Bone lesions will be considered positive if the  $^{68}\text{Ga}$ -PSMA-

HBED-CC uptake is focal and greater than physiologic bone marrow.

- Bone lesions will be classified by further by region: spine, ribs, pelvis, extremities, skull, sternum, and clavicle, as Defined in Table 12.2. These sub-regions will be correlated with reference standard results in these sub-regions, however this sub-region data will not be directly used for evaluation of the primary or secondary endpoints, but for exploratory analysis.

12.1.1.4. Prostate bed and prostate lesions will be considered positive if the Ga-PSMA-HBED-CC uptake is focal and greater than physiologic background activity of the involvement organ or anatomic site.

## 12.2. Reference standard definition:

12.2.1. Histopathology/Biopsy will be the primary determinate of tissue positivity and negativity for prostate cancer disease. Pathology date, organ, and location as well as any notes related to the pathology will be obtained from the subject chart. The anatomical region/sub-region the pathology occurred in will be assigned by the investigator team:

Ga-PSMA-HBED-CC positive findings are aimed to be confirmed by histopathology/biopsy if clinically feasible. Pathology performed 60 days before or after the Ga-PSMA-HBED-CC PET will be available for correlation.

Histopathological procedures and biopsies will be performed as clinically indicated and as per institutional protocol.

12.2.1.1. Lymph Nodes, Visceral Lesions, and Bone Lesions positive for disease by pathology.

- Lesions with positive pathologic confirmation will be regarded as positive for disease. The regionality of the resected tissue will be assigned into respective regions and sub-regions as described above in Table 12.2.

12.2.1.2. Lymph Nodes and Visceral Lesions negative for disease by pathology.

- Tissue removed and negative for pathology are considered negative for prostate cancer disease, unless subsequent conventional imaging or Ga-PSMA-HBED-CC PET imaging demonstrates that targeted tissue were not resected. In this case:

- i. Subjects can be rescanned with dedicated CT, MRI, or Ga-PSMA-HBED-CC PET/CT to determine if the suspicious Ga-PSMA-HBED-CC tissue was removed. If the tissue is confirmed as removed, this is considered negative for disease.

ii. If  $^{68}\text{Ga}$ -PSMA-HBED-CC PET/CT positive tissue is still present, a needle biopsy can be pursued at the discretion of the treating physician. Images of the procedure will be reviewed to determine if the correct tissue was biopsied.

- If the  $^{68}\text{Ga}$ -PSMA-HBED-CC PET/CT positive tissue was biopsied, a negative pathologic finding of the biopsied tissue is considered negative for disease.
- If the  $^{68}\text{Ga}$ -PSMA-HBED-CC PET/CT positive tissue was biopsied, a positive pathologic finding of the biopsied tissue is considered positive for disease.
- If biopsy or re-biopsy is not performed, or the wrong tissue was biopsied, change in node size as measured by conventional imaging and as defined below will be the criteria by which disease status will be defined.

12.2.1.3. Bone lesions: Given the high rate of false negative biopsies for osseous metastases in subjects with prostate cancer, subjects with negative bone biopsies of  $^{68}\text{Ga}$ -PSMA-HBED-CC PET positive lesions will be further evaluated:

- If pathology demonstrates an alternative diagnoses that is known to be  $^{68}\text{Ga}$ -PSMA-HBED-CC positive (eg Renal Cell Carcinoma metastases, Paget's disease), then this will be considered negative for disease.
- If pathology is indeterminate, then follow-up imaging as described below will be performed as per clinical standards at the site.

12.2.1.4. Although not routinely performed during standard practice, immunohistochemical staining for PSMA of tumor specimens (primary and lymph node metastases) may be performed, although not required.

12.2.1.5. All regions not sampled for biopsy/histopathology will be designated as indeterminate for disease by pathology. Conventional imaging follow-up may be used in these cases to determine tissue status.

12.2.2. Follow-up Imaging will be used as a secondary assessment for prostate cancer in the event pathology information is not available:

All subjects will be tracked for follow-up conventional imaging between 3-12 months post  $^{68}\text{Ga}$ -PSMA-HBED-CC (dedicated CT, MRI and/or bone scan) as per site standard of care. If no follow-up imaging has been performed within the 9 months following the  $^{68}\text{Ga}$ -PSMA-HBED-CC scan, then the research study will pay for an additional follow-up CT scan to be performed in the 9-12

month window post-Ga-PSMA-HBED-CC scan. Follow up imaging will only be performed on subjects that have positive Ga-PSMA-HBED-CC findings because conventional imaging assessment for disease is primarily targeting suspicious lesions identified by Ga-PSMA-HBED-CC PET/CT. Interpretation of follow-up imaging will be performed by local read. Preferably, the follow-up conventional imaging should be the same modality/modalities as the initial staging work-up to allow for reproducible and accurate comparisons. Conventional imaging standards as described below will be used to determine tissue positive for prostate cancer disease. Conventional imaging will not be used to determine negative prostate cancer disease regions due to its inherently low negative predictive value.

Tissue positive for prostate cancer disease based on follow-up imaging:

12.2.2.1. Lymph nodes will be assessed by change in size.

i. Positive for disease:

- a. -For subjects undergoing systemic treatment (alone or in combination with targeted treatment): If on post-treatment follow-up imaging within 3-12 months, visually suspicious lymph nodes seen on CT or MRI decrease by more than 30% in short axis diameter and PSA declines by more than 50%.
  - If PSA increases by more than 25% (PCWG3 definition of recurrence) on systemic therapy, then an increase in the size of lesion by more than 20% in the short axis diameter will be considered a positive for disease.
- b. In subjects with localized suspected lymph node(s) receiving targeted treatment without concomitant systemic treatment there are two ways to achieve positive for disease designation:
  - If the subject shows a decrease of PSA by greater than 50% after targeted treatment and the lymph node does not enlarge (change in size less than 20% in the short axis diameter or less than 3 mm increase in short axis diameter) [OR]
  - If on post-treatment follow-up imaging within 3-12 months, lymph nodes seen on CT or MRI decrease by more than 30% in short axis diameter (with a minimum of 3 mm in change in size)
- c. For untreated subjects: If on follow-up imaging within 3-12 months, lymph nodes seen on CT or MRI increase by more than 20% in short axis diameter (with a minimum of 3 mm in change in size).

ii. Negative for disease:

- Conventional Imaging follow-up will not be used for assessment of negativity for disease.

iii. Indeterminate for disease

- Regions with no lymph nodes determined to be positive by the conventional imaging criteria described above and without pathology will be designated regions indeterminate for prostate cancer disease.
- Subjects that have had neither pathology sampling, nor conventional imaging follow up will have all regions designated as indeterminate for disease by reference standard.

12.2.2.2. Visceral lesions (non-lymph node soft tissue or organ) and prostate bed and prostate lesions will be assessed by change in size.

i. Positive for disease:

- a. For subjects undergoing systemic treatment (alone or in combination with targeted treatment): If on post-treatment follow-up imaging within 3-12 months, visually conspicuous lesions seen on CT or MRI decrease by more than 30% in long axis diameter and PSA declines by more than 50%.
  - If PSA increases by more than 25% (PCWG3 definition of recurrence) on systemic therapy, then an increase in the size of lesion by more than 20% in the long axis diameter will be considered positive for disease.
- b. In subjects with localized suspected lesions(s) receiving targeted treatment without concomitant systemic treatment there are two ways to meet positive disease criteria:
  - If the subject demonstrates a decrease of PSA by greater than 50% after targeted treatment [OR]
  - If on post-treatment follow-up imaging within 3-12 months, lesions seen on CT or MRI decrease by more than 30% in long axis diameter (with a minimum of 3 mm in change in size)
- c. For untreated subjects: If on follow-up imaging within 3-12 months, lesions seen on CT or MRI increase by more than 20%

in long axis diameter (with a minimum of 3 mm in change in size).

ii. Negative for disease:

- Conventional Imaging follow up will not be used for assessment of negativity for disease

iii. Indeterminate for disease

- Regions with no visceral lesions determined to be positive by the conventional imaging criteria described above and without pathology will be designated as visceral regions indeterminate for prostate cancer disease.
- Prostate bed and prostate regions not determined to be positive by the conventional imaging criteria described above and without pathology will be designated as prostate regions indeterminate for prostate cancer disease.
- Subjects that have had neither pathology sampling, nor conventional imaging follow up will have all prostate and visceral regions designated as indeterminate for disease by reference standard.

12.2.2.3. Bone lesions will be considered:

i. Positive for disease on baseline assessment:

- Any positive sclerotic lesion on the CT portion of the Ga-PSMA-HBED-CC PET or on a separate CT obtained  $\leq$  30 days before or after the PET/CT.
- Focal uptake on the baseline bone scan performed within one month of Ga-PSMA-HBED-CC PET.
- Any MRI lesion in bone read as positive on the initial MRI performed within one month of Ga-PSMA-HBED-CC PET.

ii. Positive for disease on follow up:

- Any new positive sclerotic lesion on CT within 12 months of Ga-PSMA-HBED-CC PET scan
- Any new MRI bone lesion within 12 months of Ga-PSMA-HBED-CC PET scan
- Any new focal uptake in bone within 12 months of Ga-PSMA-HBED-CC PET scan

- In subjects with localized suspected bone lesion(s) receiving targeted treatment without concomitant systemic treatment:
- If the subject demonstrates a decrease of PSA by greater than 50% after targeted treatment.

iii. Negative for disease:

- Conventional Imaging follow up will not be used for assessment of negativity for disease

iv. Indeterminate for disease:

- Regions with no bone lesions determined to be positive by the conventional imaging criteria described above and without pathology will be designated bone regions indeterminate for prostate cancer disease.

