#### 13.2.1. True positive patient:

13.2.1.1. **Ga PSMA-HBED-CC PET/CT positive for a regional node by internal blind reader:** pathology at prostatectomy is positive for a regional node that correlates in location to the PET images (location on pathology is determined by the urologist at the time of the surgery). Only one node needs to correspond between imaging and pathology for a patient to be considered a true positive.

13.2.1.2. **Ga PSMA-HBED-CC PET/CT positive for regional nodes by internal blind reader,** pathology negative for regional nodes, imaging after prostatectomy demonstrates the same node was not removed at surgery, and follow-up biopsy or imaging demonstrates presence of nodal disease as defined in Section 12.2.1.2 .

13.2.1.3. **Conventional imaging criteria for positive node on follow-up imaging:** imaging within 3-12 months, the node decreases by more than 30% (for patients undergoing systemic treatment or focal therapy at this site) or increase by more than 20% in short axis diameter in the absence of treatment (with a minimum of 3 mm in change in size) as defined in Section 12.2.2.1 .

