13.3.2. True negative region

13.3.2.1.  **$^{68}\text{Ga}$  PSMA-HBED-CC PET negative for extra-pelvic node metastases by internal blind reader** – and pathology (if available) negative for disease, and, extra-pelvic node not positive for disease by imaging.

13.3.2.2.  **$^{68}\text{Ga}$  PSMA-HBED-CC PET negative for visceral metastases by internal blind reader** – and pathology (if available) negative for disease, and, visceral lesion not positive for disease by imaging.

13.3.2.3.  **$^{68}\text{Ga}$  PSMA-HBED-CC PET negative for osseous metastases by internal blind reader** - and pathology (if available) negative for disease, and, osseous lesion not positive for disease by imaging.

13.3.3. False positive region:

13.3.3.1.  **$^{68}\text{Ga}$  PSMA-HBED-CC PET positive for extra-pelvic nodes by internal blind reader**, pathology (if available) is negative, and imaging after prostatectomy demonstrates that node is not positive for disease.

13.3.3.1.1.  **$^{68}\text{Ga}$  PSMA-HBED-CC PET positive for regional node by internal blind reader**, but pathology (if available) is positive for node but in a different nodal region than the node seen on PSMA PET.

13.3.3.2. **PSMA-HBED-CC PET positive for visceral lesion by internal blind reader**, pathology (if available) is negative, and imaging after prostatectomy demonstrates that the visceral lesion is not positive for disease.

13.3.3.2.1.  **$^{68}\text{Ga}$  PSMA-HBED-CC PET positive for visceral lesion by internal blind reader**, but pathology (if available) is positive for visceral lesion but in a different region than the visceral region seen on PSMA PET.

13.3.3.3.  **$^{68}\text{Ga}$  PSMA-HBED-CC PET positive for osseous lesion by internal blind reader**, pathology (if available) is negative, and imaging after prostatectomy demonstrates that the osseous lesion is not positive for disease

13.3.3.3.1.  **$^{68}\text{Ga}$  PSMA-HBED-CC PET positive for osseous lesion by internal blind reader**, but pathology (if available) is positive for osseous lesion but in a different region than the osseous region seen on PSMA PET.

13.3.4. False negative region:

13.3.4.1.  **$^{68}\text{Ga}$  PSMA-HBED-CC PET negative for extra-pelvic nodes**

by internal blind reader, and pathology (if available) positive for that node, or, extra-pelvic node positive for disease by imaging as defined in Section 12.2.2.1.

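### Section 12.2.2.1.i.b gives no imaging route to positive for a node that enlarges after targeted treatment alone; its fate then differs between sections 12.2.2, 13.2 and 13.3

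*Combined protocol and SAP*

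**What the plan says.** Section 12.2.2.1.i of the combined protocol and SAP sets three imaging rules for calling a lymph node diseased, chosen by treatment received.

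- Rule (a), systemic treatment, with or without targeted treatment: shrinkage above 30% with a PSA fall above 50%, or growth above 20% when PSA rises by more than 25%.
- Rule (b), targeted treatment only: "In subjects with localized suspected lymph node(s) receiving targeted treatment without concomitant systemic treatment there are two ways to achieve positive for disease designation". The first is "If the subject shows a decrease of PSA by greater than 50% after targeted treatment and the lymph node does not enlarge", where not enlarging means "change in size less than 20% in the short axis diameter or less than 3 mm increase in short axis diameter". The second is shrinkage above 30%, minimum 3 mm.
- Rule (c), untreated subjects: "lymph nodes seen on CT or MRI increase by more than 20% in short axis diameter", minimum 3 mm, with no PSA condition.

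Section 13.2.1.3 restates this for the primary endpoint. Shrinkage counts under systemic treatment or focal therapy at the site, and growth counts as an "increase by more than 20% in short axis diameter in the absence of treatment".

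The visceral rule, 12.2.2.2.i.b, also says "there are two ways to meet positive disease criteria": a PSA fall above 50% with no size condition, or shrinkage above 30% (minimum 3 mm).

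Sections 12.2.2, 12.2.2.1.ii-iii and 12.2.2.2.ii-iii say that follow-up imaging does not establish absence of disease, and that a region with no positive lesion and no pathology is indeterminate. Section 13.3.3.1 nevertheless scores a PET-positive extra-pelvic node as a false positive when pathology, if available, is negative and "imaging after prostatectomy demonstrates that node is not positive for disease".

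**The concern.** Growth is evidence of disease in untreated men and, with a PSA rise, in men on systemic treatment. After targeted treatment alone it leads nowhere, and the plan gives no reason. A node that PET found correctly and that then progresses cannot be confirmed by imaging, whereas one that responds can.

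The resulting loss is one-sided. In the primary analysis it removes PET-positive patients, while false negatives are fixed by surgical pathology under 13.2.4.1 and remain. If the lost nodes are disease, sensitivity falls for a reason unrelated to the scan. PPV falls too if there is any false positive. Section 13.1 says these estimates will help set the sensitivity used to power a larger study.

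**Working it through.** **Scale of the plan's own precision.** Section 13.1 has no figure for this rule, but its half-widths give a yardstick: 1.96 × √(p(1−p)/30) gives 16.4, 15.5, 14.3, 12.8 and 10.7 points at 70, 75, 80, 85 and 90%, matching its table.

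**Does rule (b) admit growth?** If the short axis grows by at least 20% and at least 3 mm, both alternatives in the definition of not enlarging fail, so the first route is closed. The second route needs shrinkage. No PSA value changes this. Examples under the three rules as written:

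| Short axis | Change | PSA | (a) | (b) | (c) |
|---|---|---|---|---|---|
| 8 to 12 mm | +50%, +4 mm | +40% | positive | not positive | positive |
| 8 to 12 mm | +50%, +4 mm | −60% | not positive | not positive | positive |
| 8 to 10.5 mm | +31%, +2.5 mm | −60% | not positive | positive | not positive |
| 8 to 10.5 mm | +31%, +2.5 mm | +40% | positive | not positive | not positive |
| 20 to 23.5 mm | +17.5%, +3.5 mm | −60% | not positive | positive | not positive |

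A grid of baseline 3-25 mm, follow-up 3-40 mm and PSA change −95% to +200% contains 123,600 combinations with growth above 20% and at least 3 mm. Rule (b) calls 0 positive, rule (a) 72,100 (those with a PSA rise above 25%) and rule (c) all 123,600. These counts describe the logic and are not frequencies.

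**Primary endpoint.** Under 12.2.1.2, size change decides only when a PET-positive node was left behind and was not biopsied, or the wrong tissue was biopsied. A growing node under rule (b) then fails 13.2.1.2 and 13.2.1.3. It cannot be a false positive under 13.2.3.1, which needs the node to have gone. The patient is non-evaluable under 13.2.5.1.

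For size, take sensitivity as TP/(TP+FN). (Section 13.1 prints false positives in the denominator, which is a separate matter.) The two pre-surgical studies summarised in section 2.3 imply these nodal prevalences:

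- 130-patient study, from sensitivity 65.9%, specificity 98.9% and accuracy 88.5%: (0.989 − 0.885)/(0.989 − 0.659) = 31.5%.
- 30-patient study, from sensitivity 64%, specificity 95% and PPV 88%: 0.88 = 0.64p/(0.64p + 0.05(1−p)), so p = 0.044/0.1208 = 36.4%.

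That is 9.5 to 10.9 node-positive men of 30. With assumed counts in that range, losing one true positive moves 8/10 = 80.0% to 7/9 = 77.8%, or 6/9 = 66.7% to 5/8 = 62.5%. Starting from 7/11 = 63.6%, losing one or two gives 6/10 = 60.0% or 5/9 = 55.6%.

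**Secondary endpoint.** Assume 4 PET-positive extra-pelvic regions, all diseased, one growing after targeted treatment without pathology. Under 13.3.3.1 read literally, PPV is 3/4 = 75%. Under 12.2.2.1.iii and 13.3.5.1 the region is non-evaluable and PPV is 3/3 = 100%. With 8 regions the two readings give 7/8 = 87.5% and 7/7 = 100%. The drop therefore comes from the conflict between these sections, not from rule (b) alone. Section 13.3.3.2 raises the same conflict for visceral lesions.

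**Unit of treatment.** Section 12.2.2.1 assigns its rules by subject, and rule (c) is for untreated subjects. Section 13.2.1.3 refers to therapy at the site. An untreated node that grows in a man given targeted treatment elsewhere may be positive under 13.2.1.3 and not positive under 12.2.2.1.

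**The case against.** The strongest reply is that the path is narrow. All men are treatment-naïve with planned prostatectomy and node dissection. To be affected in the primary analysis, a man needs a PET-positive node, negative surgical pathology, imaging showing the node was left behind, no correct biopsy, targeted treatment without systemic therapy, and growth beyond both limits within 3-12 months. The study is a descriptive pilot, and the illustrated shifts are well inside its stated half-widths. Listing exactly two routes may also be a deliberately conservative, response-based standard, since post-treatment swelling can mimic growth. All of this stands, and it limits the point to a minor one. It does not explain why growth counts under (a) and (c), nor does it settle the conflict with 13.3.3.

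A reader might infer more than the documents support:

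- That such a node can never be disease. Positive pathology makes it disease whatever its size change (12.2.1.1), and smaller growth with a PSA fall above 50% passes the first route of rule (b).
- That the visceral rule has the identical gap. It lacks a growth route, but a PSA fall above 50% suffices there even if the lesion grows.
- That an untreated node in a man treated elsewhere is definitely shut out of rule (c). That is one reading; the wording of 13.2.1.3 allows another.
- That one growing node always costs the region. Section 12.2.2.1.iii applies only where no node in the region is positive.

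**Conclusion.** The point holds as a minor gap in the reference standard. Without valid pathology, a PET-positive node that enlarges by at least 20% and at least 3 mm after targeted treatment alone has no imaging route to positive, and 13.2.1.3 repeats this for the primary endpoint.

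A reader might conclude that the primary analysis counts such a patient against PET. It does not: the patient drops out. A false-positive score is possible only for secondary regions, and only if 13.3.3.1 or 13.3.3.2 is read literally against 12.2.2.

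The direction of bias, towards lower sensitivity, assumes that the lost nodes are disease. The effect is probably small. The documents give no frequency for targeted treatment of unresected, unbiopsied nodes, so the shifts of about 2 and 4 points are illustrations, not estimates. This also assumes that targeted treatment means treatment aimed at the suspected lesion and not the study prostatectomy; the plan does not define the term.

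**What to change.** These changes concern reference-standard wording only, not patient management.

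1. In 12.2.2.1.i.b and 12.2.2.2.i.b, add a growth route parallel to rule (a): growth above 20% with a PSA rise above 25% is positive for disease. State whether the 3 mm minimum applies, since (c) has it and the growth route in (a) does not. If the sponsor prefers no growth route, say explicitly that such lesions are indeterminate.
2. Use one unit of treatment classification, the lesion site, in 12.2.2 and 13.2.1.3, and bring 13.2.1.3 into line with the amended 12.2.2.1.
3. Amend 13.3.3.1 to 13.3.3.3 so that a PET-positive region that is merely not positive on imaging, without negative pathology, is non-evaluable and not a false positive.

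The cost is a short amendment with no new data. The downside is that post-treatment swelling could meet the size limit; the PSA condition limits this.

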## 5.7. **Post-Prostatectomy Procedures**

- 5.7.1. **PSMA-positive with negative pathology.** Subjects with  $^{68}\text{Ga}$  PSMA-HBED-CC positive nodes without positive nodes on pathology, may be rescanned with CT (or MRI) to determine if the suspicious node was thought to be removed. Additionally, clinicians will have the option to order a 2nd  $^{68}\text{Ga}$  PSMA-HBED-CC PET/CT as described in Section 6.4.4.
- 5.7.2. **PSMA-positive osseous or metastatic lesions.**  $^{68}\text{Ga}$  PSMA-HBED-CC positive osseous or distant metastatic lesions will be followed by other imaging (bone scan, NaF PET, CT or MRI) at the treating physician's discretion and local standard of care.
- 5.7.3. **Biopsy.** Biopsies to determine metastases or provide information for re-staging should be performed at treating physician's discretion and per local

standard of care.

- 5.7.4. **CT or MRI.** Subjects should undergo routine standard of care imaging.
- 5.7.5. Positive disease identified by either Ga PSMA-HBED-CC PET/CT or follow-up conventional imaging will trigger locally performed anatomic measurement of lesion size(s) on both the baseline CT or MRI, and the follow-up CT or MRI of suspected site of disease.

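### New lesions on follow-up count as disease in bone but have no stated route in nodes or viscera, and 12.2.2 and 13.3 then label the same region differently

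*Combined protocol and SAP*

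**What the plan says.** **Bone.** 12.2.2.3.ii lists new findings as positive with no size condition: "Any new positive sclerotic lesion on CT within 12 months of" the PET scan, "Any new MRI bone lesion within 12 months of" it, and likewise new focal uptake.

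**Nodes.** 12.2.2.1 opens with "Lymph nodes will be assessed by change in size". For untreated men the rule is that "lymph nodes seen on CT or MRI increase by more than 20% in short axis diameter", with at least 3 mm of change. The treated-patient rules also use percentage changes, some combined with PSA.

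**Viscera.** 12.2.2.2 has the same structure in long axis; the untreated rule begins "If on follow-up imaging within 3-12 months, lesions seen on CT or MRI increase by more than 20" per cent, again with the 3 mm minimum. Neither section mentions a new lesion.

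**Measurement.** 5.7.5 calls for "measurement of lesion size(s) on both the baseline CT or MRI, and the follow-up CT or MRI".

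**Other routes to positive.** Positive pathology is enough for any lesion (12.2.1.1). After targeted treatment alone, a PSA fall above 50% is enough for viscera, and for nodes if the node does not enlarge.

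**Classification.** 13.3.2.2 makes a PET-negative visceral region a true negative when pathology, where it exists, is "negative for disease, and, visceral lesion not positive for disease by imaging"; 13.3.2.1 does the same for extra-pelvic nodes. 12.2.2.1.iii and 12.2.2.2.iii instead call a region indeterminate if it is not positive by imaging and has no pathology, and 12.2.2 says that conventional imaging does not establish negativity.

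**The concern.** A percentage change needs a starting diameter. A node or visceral lesion that is absent or unmeasurable at baseline has none, and no other imaging rule picks it up. The same event, a lesion first seen on a follow-up scan, is thus disease in bone and not disease in liver or a retroperitoneal node.

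Two kinds of region are affected. At a PET-negative site, a metastasis that PET may have missed cannot enter as a miss. At a PET-positive site, a lesion that PET showed before CT could measure it cannot confirm the PET finding. The first favours PET and the second works against it. Section 13.3 reports the three sites separately and also pools them across all regions imaged, so the pooled figures mix two reference standards. Section 13.1 names the reference standard as a particular source of uncertainty and plans to use the results to power a larger study.

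Missing baseline diameters are plausible. The study orders no contrast (5.1.3), and earlier CT or MRI is collected only if it was done (6.1.3, 6.1.4). The study follow-up CT, by contrast, uses contrast unless contraindicated (6.4.2).

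**Working it through.** **The plan's own figures.** The only computed figures are the half-widths in 13.1. With 1.96 × √(p(1 − p)/30), p = 0.80 gives 1.96 × √(0.16/30) = 14.3%, as printed, and the other four rows also reproduce. They do not bear on this point. 13.1 prints sensitivity as TP/(TP + FP), which is the formula for PPV; below I use TP/(TP + FN).

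**The size rule.** Change = 100 × (F − B)/B, where B is the baseline and F the follow-up diameter. The diameters are chosen for illustration.
- B = 4 mm, F = 8 mm: +100% and +4 mm. The untreated rule is met.
- B = 8 mm, F = 10 mm: +25% but +2 mm. Not met, because of the 3 mm minimum.
- B = 0, F = 8 mm: division by zero. The percentage is undefined.

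A new lesion could qualify later if a second scan in the window showed growth and the first follow-up scan served as baseline, but the documents do not say so.

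**Tracing a new nodal or visceral lesion on first appearance,** with no pathology and no PSA response after targeted treatment. The PET condition in 13.3.4.2 names extra-pelvic nodes; I read it as viscera, as the rest of that sentence implies.

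| Site on PET | Under 13.3 | Under 12.2.2 iii | Not reachable by imaging |
|---|---|---|---|
| Negative | True negative (13.3.2.1, 13.3.2.2) | Indeterminate | False negative: 13.3.4.1 and 13.3.4.2 refer back to 12.2.2.1 and 12.2.2.2 |
| Positive | False positive, if the imaging is taken as showing the lesion not positive (13.3.3.1, 13.3.3.2) | Indeterminate | True positive: 13.3.1.1 and 13.3.1.2 refer back to the same rules |

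In bone, the same event is a false negative in the first row and a true positive in the second.

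**Illustration, PET-negative site.** Assume 30 regions of one type, one per man, with TP true positives and no other errors. One PET-negative region develops a new lesion.
- Scored true negative: sensitivity TP/TP = 100%; NPV 100%.
- Scored indeterminate: both stay at 100%, with 29 evaluable regions.
- Scored false negative: sensitivity = TP/(TP + 1), NPV = (29 − TP)/(30 − TP).

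| TP | Sensitivity | NPV |
|---|---|---|
| 1 | 1/2 = 50% | 28/29 = 96.6% |
| 2 | 2/3 = 66.7% | 27/28 = 96.4% |
| 3 | 3/4 = 75% | 26/27 = 96.3% |
| 5 | 5/6 = 83.3% | 24/25 = 96.0% |

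**Illustration, PET-positive site.** Of 2, 3 or 5 PET-positive regions, one has a lesion that becomes visible only at follow-up and the others are true positives. Scored false positive, PPV is 1/2 = 50%, 2/3 = 66.7% or 4/5 = 80%. Scored indeterminate or true positive, PPV is 100%; the two differ only in the number of evaluable regions.

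**The case against.** A reader might infer that a new lesion at a PET-negative site is always scored a true negative. The documents do not support that. It follows from 13.3.2 read alone, whereas 12.2.2.1.iii and 12.2.2.2.iii call the region indeterminate, which could make it non-evaluable under 13.3.5.1. What stands is a conflict between the sections, and the fact that neither label is a miss.

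A reader might also infer that a new lesion can never confirm a PET-positive site. That too is more than the text says, because pathology and the PSA route remain open. For nodes the PSA route also requires that the node not enlarge, which a newly visible node may fail. Nor is a false positive certain: 13.3.3 asks for imaging that shows the lesion not to be positive, and a lesion emerging at that very site hardly shows this.

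Growth from invisible to 8 mm could be read as exceeding 20%, and 5.7.5 is a measurement instruction rather than a condition for positivity. That reading is possible. But the bone section names new lesions and the other two do not, so the text needs to say which is meant.

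Reach is limited. 12.2.2 restricts study follow-up imaging to men with positive PET findings, so a new lesion at a PET-negative site will be seen mainly in men positive elsewhere or on standard-of-care scans. The secondary analyses are descriptive. The primary endpoint rests first on surgical pathology and meets the size rule only through 13.2.1.2 and 13.2.1.3.

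Finally, a lesion first seen late may have arisen after the PET scan. That is a fair reason not to require that each one be a false negative, though the bone rule already carries the same risk.

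**Conclusion.** The concern holds in limited form. Bone has a new-lesion route and nodes and viscera do not. Without positive pathology or the PSA route, a nodal or visceral lesion with no baseline diameter cannot on first appearance become a true positive or a false negative, and 12.2.2 and 13.3 disagree on what it becomes. The nodal and visceral secondary endpoints therefore use a different reference standard from bone while being pooled with it.

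The size cannot be estimated, because the documents give no expected number of extra-pelvic nodal or visceral lesions. Under the stated assumptions, one missed lesion with 1 to 5 true positives is the difference between 100% and 50–83% sensitivity, while NPV falls only to 96.0–96.6%. These ranges show how far one region can move an estimate; they do not predict the bias. Nor do the small mean node sizes in 2.3 (4.7 mm detected, 2.7 mm missed) settle how often it will happen: they come from a prospective preoperative nodal staging study that excluded men with suspected extra-nodal disease on CT.

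**What to change.** 1. In 12.2.2.1 and 12.2.2.2, state that a node or visceral lesion not measurable at baseline is positive for disease if it newly appears on CT or MRI at a PET-positive site within 3–12 months and is read as metastatic.
2. State that a PET-negative region with such a new lesion and no pathology cannot be a true negative. Report secondary sensitivity and NPV twice: with it as a false negative, as the bone rule would have it, and with it as indeterminate.
3. Reconcile 12.2.2.1.iii and 12.2.2.2.iii with 13.3.2 and 13.3.3, so that a region not positive by imaging and without pathology has one label.
4. Report how many positives rest on new lesions alone.

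The cost is a few sentences and one extra set of descriptive results, with no new imaging. There are two drawbacks. Some new lesions may postdate the PET scan. The follow-up read is also local (12.2.2), by readers told where PET was positive (6.4.2), so confirmation at PET-positive sites is not independent of PET. Item 4 lets readers judge how much depends on such cases. The plan's 3 mm minimum should not be reused as an absolute size for a new lesion: it is defined as a change in a measured diameter.
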